7.1.2.1 Part A

During the treatment period, the following assessments will be performed (see [Appendix I](#) for the detailed schedule):

- The EQ-5D and FACT-M will be completed by subjects prior to any study related procedures at Week 7, and then once every 6 weeks thereafter while on treatment.
- Subject interviews (optional) by a trained experienced interviewer to collect subjects' current experience with their disease and its treatment (at Week 13 and at 6 months of treatment, see [Section 7.7.1](#)).
- AEs and concomitant medications will be documented at each trial visit.
- ECOG PS will be assessed at Day 1 (unless the Screening ECOG PS was performed within 3 days prior to Day 1) and at each study visit thereafter.
- Physical examinations will be performed at each treatment visit until Week 13 and every 6 weeks thereafter. Such examinations will include a comprehensive skin examination for tumor.
- Vital signs and body weight will be assessed in each treatment visit.
- A 12-lead ECG (assessed prior to infusion and 2 hours \pm 20 minutes after the end of infusion) will be assessed at each treatment visit up to and including Week 13, and every 6 weeks thereafter until 18 months, after which subjects no longer require on treatment ECGs.
- The laboratory hematology, hemostaseology will be assessed at each visit. Core serum chemistry tests will be assessed at Weeks 1, 7, 9, and 11 and after Week 13, every 2 weeks thereafter and full serum chemistry (including core chemistry) will be assessed at Weeks 3, 5, and 13 and then every 6 weeks thereafter. In addition, for subjects with liver metastases at Baseline, samples for ALT, AST, total bilirubin, and alkaline phosphatase determination will be collected at Weeks 2, 4, and 6. A basic urinalysis (dipstick) will be performed at each on treatment visit. If the basic urinalysis is abnormal, a full urinalysis should be performed.
- A urine β -HCG pregnancy test will be performed at each treatment visit (before each administration of the study drug) for females of childbearing potential.
- Tumor evaluation (see [Section 7.3](#)) will be performed at Week 7, and then once every 6 weeks thereafter, with a tumor assessment visiting time window of 5 days prior to dosing. After Week 55 (12 months) from the first treatment, tumor assessments will be every 12 weeks.

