Because of the high number of participating centers and the anticipated small number of subjects receiving trial treatment in each center, data will be pooled across centers. The factor center will not be considered for subgroup analyses.

Definition of baseline:

The last non-missing measurement prior to the first study drug administration will be used as the baseline measurement, if not otherwise specified. Additionally, ECG baseline will be derived from the visit where at least HR, PR, QRS, and QT are not missing. QTcF will be derived based on HR and QT. The average of the replicate measurements (prior infusion and post infusion) should be used in deriving baseline values for each parameter.

Definition of study day/treatment day:

Treatment day is defined relative to the first study drug administration.

Treatment day 1 defines the first study drug administration date, the day before is defined as treatment day -1 (no treatment day 0 is defined).

Definition of on-treatment period:

On-treatment period is defined as the time from the first study drug administration to the last drug administration date + 30 days or earliest date of subsequent anti-cancer drug therapy – 1 day, whichever occurs first, unless otherwise stated. If the earliest date of subsequent anticancer drug therapy was a partial date and only day was missing, it was imputed as the last day of the month. If both day and month were missing, no imputation was performed. The imputed date was used for defining on-treatment period as well as confirming CCI

Unscheduled visits:

Data collected at unscheduled visits will be included and analyzed for both safety and efficacy analyses in the same fashion as the data collected at scheduled visits.

Data collected after re-initiated treatment:

Data collected after re-initiation of treatment will not be included for safety and efficacy analyses except for overall survival and disposition.

Visit Window:

The assignment of visit window is described in Table 1 for the purpose of by-visit analyses of safety data:

- Baseline will be derived as described above.
- Both scheduled and unscheduled assessments are included for visit windowing.

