- No visit windowing will be performed at Discontinuation, End-of-Treatment, or Safety Follow-up visits for laboratory, vital sign, ECG data, and 2hr post dose assessment on Week 1 Day 1 for ECG data. Instead, the earliest non-missing observation among the unscheduled or scheduled assessments for each visit (Discontinuation, End-of-Treatment, and Safety Follow-up) will be used for the analysis. For 2hr post dose assessment on Week 1 Day 1 ECG data, the earliest non-missing observation on Week 1 Day 1 will be used for the analysis.
- If there are multiple assessments for any specified visit and some of them are from scheduled visits with non-missing assessment results, the assessment from scheduled visit that is closest to the planned study day will be used for analysis.
- If there are multiple assessments for any specified visit and none of them are from scheduled visits, the assessment with non-missing results and closest to the planned study day will be used for analysis.
- If there are two or more unscheduled assessments with non-missing results and the same distance to the planned study day, the assessment prior to the planned study day will be used in deriving visit window. For example, if the lab assessment was done on both study day -1 and 1, then the assessment on -1 study day will be used for visit windowing.
- For ECG assessment associated with study drug dose, only assessments where time point (prior to infusion or 2 hr after infusion) are not missing will be considered for the analysis.

Table 1 Visit Window Definition for Safety Assessment

| Assigned Study Day (Inclusive) | | Planned Study Day (AWTARGET) | Analysis Visit (N) (AVISITN) | Analysis Visit (AVISIT) | Assessment |
|--------------------------------|-----------|------------------------------|------------------------------|-------------------------|----------------------|
| From (AWLO) | To (AWHI) | | | | |
| ~ | 1 | | 1 | Baseline | Lab, Vital Sign, ECG |

| | | | | | |
|-----|-----|-----|----|---------------------|----------------------|
| 1 | 1 | 1 | 2 | Week 1 Day 1* | ECG |
| 5 | 11 | 8 | 3 | Week 2 Day 5-11 | Core Serum Chemistry |
| 12 | 18 | 15 | 4 | Week 3 Day 12-18 | Lab, Vital Sign, ECG |
| 19 | 25 | 22 | 5 | Week 4 Day 19-25 | Core Serum Chemistry |
| 26 | 32 | 29 | 6 | Week 5 Day 26-32 | Lab, Vital Sign, ECG |
| 33 | 39 | 36 | 7 | Week 6 Day 33-39 | Core Serum Chemistry |
| 40 | 50 | 43 | 8 | Week 7 Day 40-50 | Lab, Vital Sign, ECG |

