| 51 | 64 | 57 | 10 | Week 9 Day 51-64 | Lab, Vital Sign, ECG |
| 65 | 78 | 71 | 12 | Week 11 Day 65-78 | Lab, Vital Sign, ECG |
| 79 | 92 | 85 | 14 | Week 13 Day 79-92 | Lab, Vital Sign, ECG |
| 93 | 106 | 99 | 16 | Week 15 Day 93-106 | Lab, Vital Sign |
| 107 | 120 | 113 | 18 | Week 17 Day 107-120 | Lab, Vital Sign |
| 121 | 134 | 127 | 20 | Week 19 Day 121-134 | Lab, Vital Sign |
| 107 | 148 | 127 | 20 | Week 19 Day 107-148 | ECG |
| 135 | 148 | 141 | 22 | Week 21 Day 135-148 | Lab, Vital Sign |
| 149 | 162 | 155 | 24 | Week 23 Day 149-162 | Lab, Vital Sign |
| 163 | 176 | 169 | 26 | Week 25 Day 163-176 | Lab, Vital Sign |
| 149 | 190 | 169 | 26 | Week 25 Day 149-190 | ECG |
| 177 | 190 | 183 | 28 | Week 27 Day 177-190 | Lab, Vital Sign |
| 191 | 204 | 197 | 30 | Week 29 Day 191-204 | Lab, Vital Sign |
| 205 | 218 | 211 | 32 | Week 31 Day 205-218 | Lab, Vital Sign |
| 191 | 232 | 211 | 32 | Week 31 Day 191-232 | ECG |

* Only applies to 2 hr post dose.

Calculation of duration:

Duration will be calculated by the difference of start and stop date + 1 (e.g. survival time (days) = date of death – date of first study treatment + 1), unless otherwise specified.

Conversion of days to months or years:

The following conversion factors will be used to convert days into months or years: 1 month = 30.4375 days, 1 year = 365.25 days.

Significance level:

The overall significance level is 2.5% one-sided. The confirmatory statistical test for the primary efficacy endpoint analysis is described in Section 16.1 along with procedures for controlling the overall type I error rate. All other statistical analyses performed on the secondary and other endpoints defined in this SAP are exploratory.

Confidence intervals will be two-sided with a confidence probability of 95%, if not otherwise specified.

Presentation of continuous and qualitative variables:

Continuous variables will be summarized using descriptive statistics i.e., number of non missing values and number of missing values, [i.e. n (missing)], mean, median, standard deviation (StdDev), minimum, maximum and first and third quartile (Q1 and Q3).

Qualitative variables will be summarized by counts and percentages. Unless otherwise stated the calculation of proportions will include the missing category. Therefore counts of missing observations will be included in the denominator and presented as a separate category.

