17.5 Other Safety or Tolerability Evaluations

17.5.1 ECG

The incidence and percentage of subjects with potentially clinically significant abnormalities (PCSA) for 12-lead Electrocardiogram (ECG) parameters will be summarized during the on-treatment period. The PCSA criteria are provided in Table below.

Table 8 Potentially Clinically Significant Abnormalities criteria for ECG

| Test | Potentially Clinically Significant Abnormalities (PCSA) Criteria |
|------------------------------------|--|
| Heart Rate (HR) | ≤ 50 bpm and decrease from baseline ≥ 20 bpm ≥ 120 bpm and increase from baseline ≥ 20 bpm |
| PR Interval | ≥ 220 ms and increase from baseline ≥ 20 ms |
| QRS | ≥ 120 ms |
| QTcF and QTcB absolute | Interval >450 msec and interval ≤ 480 msec Interval >480 msec and interval ≤ 500 msec Interval >500 msec |
| QTcF and QTcB change from baseline | Increase from baseline > 30 msec and ≤ 60 msec Increase from baseline > 60 msec |

QTc will be corrected based on Fridericia's formula for QTcF and Bazett's formula for QTcB ($QTcF = QT / \sqrt[3]{RR}$ and $QTcB = QT / \sqrt{RR}$) where $RR=60/HR$. Baseline QTcF and QTcB will be derived from the visit that other ECG parameters are flagged as baseline. If there are multiple assessments at the same visit and time point, the average will be calculated for each parameter and used for the analysis.

Quantitative data for HR, PR, QRS, QTcF and QTcB will also be examined for trends using descriptive statistics (n, missing, mean, StdDev, median, Q1, Q3, minimum, maximum, and confidence interval) of actual values with 95%CI, absolute changes from baseline to each visit with 90%CI based on visit windows specified in Section 11.

Listings of 12-lead ECGs will be provided with all relevant information and derived variables.

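### Part A SAP: the ECG baseline sentence can be read to include the post-infusion ECG, which would halve the Day 1 2-hour change and shift all later changes for subjects with a Day 1 baseline

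*SAP*

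**What the plan says.** Part A SAP, Section 11, sets a general rule: "The last non-missing measurement prior to the first study drug administration will be used as the baseline measurement, if not otherwise specified". It then adds that ECG baseline comes from a visit at which HR, PR, QRS and QT are all present, and continues: "The average of the replicate measurements (prior infusion and post infusion) should be used in deriving baseline values for each parameter".

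Other places bear on the same point:

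- **Part A SAP 17.5.1**, directly after the statement on which visit supplies baseline QTcF and QTcB: "If there are multiple assessments at the same visit and time point, the average will be calculated for each parameter".
- **Part A SAP Section 11, visit windows**, for ECGs linked to a dose: "only assessments where time point (prior to infusion or 2 hr after infusion) are not missing will be considered for the analysis".
- **Part A SAP Table 1** lists Baseline (a window running through Day 1) and, separately, a Week 1 Day 1 ECG visit with the footnote "Only applies to 2 hr post dose".
- **Protocol 7.1.2.1** (and Appendix I, Part A, footnote i) schedules an ECG before infusion and another about 2 hours after its end. This pair "will be assessed at each treatment visit up to and including Week 13, and every 6 weeks thereafter until 18 months". No number of replicates per time point is given.

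Two outputs in Part A SAP 17.5.1 use the baseline. The incidence of potentially clinically significant abnormalities (PCSA) "will be summarized during the on-treatment period". The descriptive statistics include "absolute changes from baseline to each visit with 90%CI based on visit windows specified in Section 11".

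**The concern.** A baseline for a drug-effect comparison should hold only pre-treatment readings. The sentence names post-infusion readings as an input, and the general rule gives way wherever something else is specified. On Day 1 the only scheduled pair that fits the parenthesis is the pre-infusion ECG and the 2-hour ECG. An analyst could therefore average these two, and the 2-hour reading would then be compared with a value that contains it. The stake is the accuracy of a descriptive safety summary. A real QTc, HR or PR change after the first infusion would look smaller than it was, and later changes would carry an offset that differs from subject to subject.

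**Working it through.** The plan states no figure for this point, so there is nothing to reproduce. The check is algebra on the two readings.

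**Inputs.** One ECG before and one 2 hours after the Day 1 infusion (Protocol 7.1.2.1; one reading per time point is an assumption). 88 treated subjects (Part A SAP Section 7). PCSA criteria from Part A SAP 17.5.1, Table 8: QTc increase >30 to ≤60 ms and >60 ms; HR ≤50 bpm with a decrease ≥20, or ≥120 bpm with an increase ≥20; PR ≥220 ms with an increase ≥20 ms. Values of D, means and SDs are assumptions.

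**Effect on one subject.** Let D = 2-hour reading − pre-dose reading, and C = any later reading − pre-dose reading.

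- Averaged baseline = (pre + pre + D)/2 = pre + D/2.
- Reported 2-hour change = D − D/2 = D/2.
- Any other reported change = C − D/2.

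Halving is exact for one reading at each time point, or equal numbers. With two pre-dose readings and one post-dose reading pooled, 2/3 of D would be kept. If QTcF is computed from averaged HR and QT, halving is approximate: HR 70 to 80 and QT 390 to 400 give D = 29.7 ms, reported as 14.8.

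**QTc change bands.** Let Cmax be the largest on-treatment increase from the pre-dose reading. The reported maximum is Cmax − D/2, so both cut-offs move by D/2.

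| D (ms) | Effect at the 30 ms cut-off | Effect at the 60 ms cut-off |
|---|---|---|
| +10 | Cmax >30 to 35 not flagged | Cmax >60 to 65 placed in the lower band |
| +20 | Cmax >30 to 40 not flagged | Cmax >60 to 70 placed in the lower band |
| −10 | Cmax >25 to 30 flagged in error | Cmax >55 to 60 placed in the upper band |
| −20 | Cmax >20 to 30 flagged in error | Cmax >50 to 60 placed in the upper band |

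**HR and PR.** The change part of an increase criterion becomes 20 + D/2; for an HR decrease it becomes 20 − D/2. With D = +10 these are 25 and 15. The absolute conditions do not depend on baseline, so only subjects who already meet them can be reclassified.

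**By-visit mean at Day 1.** If all 88 subjects have a Day 1 baseline, the 90% CI half-width is t(0.95, 87) × SD/√88. For SD 10, 15 and 20 ms this is 1.77, 2.66 and 3.54; after halving it is 0.89, 1.33 and 1.77. With an assumed mean of 8 ms and SD 15, the result 8 (5.34 to 10.66) would be reported as 4 (2.67 to 5.33).

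If only a share f has a Day 1 baseline, and D does not depend on this, the reported mean is (1 − f/2) of the true mean: 75%, 60% and 50% for f = 0.5, 0.8 and 1.0.

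**How much of the on-treatment record is the 2-hour reading.** Seven visits through Week 13 (Days 1, 15, 29, 43, 57, 71, 85) × 2 readings = 14. Less the Day 1 pre-dose reading, 13 remain, of which the Day 1 2-hour ECG is one. The other 12 carry the −D/2 shift rather than the halving.

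**The case against.** The best reply is that the sentence is loose wording for averaging replicates within each time point. A pre-dose ECG and one taken 2 hours after infusion are different time points, not replicates. The ECG text opens with *Additionally*, which suggests that it adds to the pre-dose rule. Section 17.5.1 is the ECG-specific section, and it confines averaging to one visit and one time point immediately after discussing baseline QTc. Table 1 gives the 2-hour reading its own visit. The Part B SAP (version 3.0) later dropped its references to replicate ECGs and uses a pre-treatment baseline, though its change log gives no reason. The protocol's silence on replicates also does not prove that none were taken.

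Most of this stands. The benign reading is plausible, and an analyst who sees all the passages may well adopt it. It does not, however, remove the post-infusion readings from the baseline rule, and nothing in the Part A SAP says which passage governs.

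A reader might also infer that subjects with a QTc rise just above 60 ms would disappear from the table, or that any HR or PR change near 20 would be misclassified. Neither follows. With D above zero, a rise just above 60 ms falls into the lower band. The HR and PR criteria require an absolute value as well.

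**Conclusion.** The point holds as a conflict of wording with a definite consequence if the sentence is applied as it can be read. The Day 1 2-hour change would be halved and later changes shifted by −D/2, for subjects with a Day 1 baseline and one reading per time point.

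A stronger conclusion, that the Part A ECG tables are wrong or that an analyst was bound to average those two readings, is not supported. The documents do not show the program, and they contain rules that point the other way. Nor can one say that abnormalities were under-counted overall: the error runs in either direction with the sign of D, and no ECG effect, SD or share of Day 1 baselines is given.

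The absolute QTc and QRS criteria, subjects with a screening baseline, Part B and all efficacy analyses are untouched. Priority is low, because these are descriptive safety outputs in a single-arm study.

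**What to change.** Replace the averaging sentence in Part A SAP Section 11 with: *ECG baseline is the average of any replicate readings at the last time point before the first infusion with HR, PR, QRS and QT non-missing; post-infusion readings are not used.* Keep the Day 1 2-hour ECG as a post-baseline visit only, as Table 1 already has it.

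Then check how the Part A ECG baseline was programmed. The protocol already cites published Part A results, so rewording alone would not alter an analysis already run; the check is what matters. If pre- and post-infusion readings were averaged, re-run the change-from-baseline summaries and the change-based PCSA counts, and document the correction. If they were not, nothing needs re-running.

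The cost is one sentence and a short programming check, with a small re-run of descriptive tables only in the first case.

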12.1 Disposition of Subjects and Discontinuations

The following will be summarized overall:

Subject disposition:

- Number of subjects screened (i.e. subjects who gave informed consent)
- Number of subjects per reason of non-eligibility at end of screening visits
- Number of subjects in the ITT population
- Number of subjects in the Safety population
- Number of subjects in the PP population
- Number of subjects still on treatment
- Number of subjects off-treatment overall and by the main reason for discontinuation
- Number of subjects who discontinued the treatment but are still in follow-up
- Number of subjects who discontinued the trial overall and by the main reason for discontinuation

In addition, the following will be summarized:

- Number and percentage of subjects by region (Europe, North America, Latin America, Asia, Australia), by country within region and by center for each of the analysis set (Screening, ITT (Safety) and PP analysis set).

12.2 Protocol Deviations

Protocol deviations will be listed and summarized based on the ITT.

All important protocol deviations that impact the safety of the subjects and/or the conduct of the study and/or its evaluation will be reported. These include:

- subjects that are dosed on the study despite not satisfying the inclusion criteria;
- subjects that develop withdrawal criteria while on the study but are not withdrawn;
- subjects that receive the wrong treatment or an incorrect dose;
- subjects that receive an excluded concomitant medication;

- Deviation from GCP.

Important protocol deviations will be determined for all subjects by either medical review processes or programming based on the inclusion/exclusion criteria or other criteria presented in the protocol.

All important protocol deviations should be documented in CDISC datasets whether identified through sites monitoring, medical review or programming. Important Protocol Deviations to be identified by programming as well as all clinically Important Protocol Deviations are listed and described in Appendix I. They will be presented in the summary table and in a data listing.

13 Demographics and Other Baseline Characteristics

Analysis sets: ITT analysis set / Safety analysis set

13.1 Demographics

Demographic characteristics will be summarized as follows:

- Demographic characteristics
 - Gender: Male, Female
 - Race: White, Black or African American, Asian, American Indian or Alaska Native, Native Hawaiian or other Pacific Islander, Other, Unknown
 - Ethnic origin: Hispanic/Latino (Yes/No), Japanese (Yes/No)
 - Age (years): summary statistics
 - Age categories : < 65 years, ≥ 65 years
 - 65-74, 75-84, ≥ 85
 - Height (cm)
 - Weight (kg)
 - Body Mass Index (BMI) (kg/m²)
 - Pooled Region:
 - North America
 - Europe
 - Rest of the World
 - Geographic Region:
 - North America
 - Latin America
 - Western Europe
 - Eastern Europe
 - Australia
 - Asia
 - Eastern Cooperative Oncology Group (ECOG) Performance Status

Specifications for computation:

- Age [years]:
 - (date of given informed consent - date of birth + 1) / 365.25
 - In case of missing day of birth, day is replaced by 15
 - In case only year of birth is given: Age [years]: (year of given informed consent - year of birth)

The integer part of the calculated age will be used for reporting purpose.

- BMI (kg/m²) = Weight(kg)/[Height(m)]².

13.2 Medical History

Medical history will be coded using the most current available version of Medical Dictionary for Regulatory Activities (MedDRA). Medical history will be summarized as the numbers and percentages of subjects by MedDRA preferred term (PT) as event category and MedDRA primary system organ class (SOC) as summary category. Each subject will be counted only once within each PT or SOC.

Medical history will be displayed in terms of frequency tables: ordered by primary SOC and PT in alphabetical order.

13.3 Other Baseline Characteristics

13.3.1 Disease Characteristics

Information on disease characteristics collected on “Disease History” eCRF page will be summarized as follows:

- Site of primary tumor
- Tumor size
- Peripheral margin status
- Deep margin status
- Lymphovascular invasion
- Extracutaneous extension
- Time since initial diagnosis (months), defined as (date of the first study treatment – date of initial diagnosis)/30.4375
- Time since first metastatic disease (months), defined as (date of the first study treatment – date of the first occurrence of metastatic disease)/30.4375
- Time since first locally advanced disease (months), defined as (date of the first study treatment – the date of the first occurrence of locally advanced disease)/30.4375

- Time since last progression of disease prior to study entry (months), defined as (date of the first study treatment –date of the last progression of disease)/30.4375
- TNM classification at initial diagnosis
- TNM classification at study entry
- Additional clinically relevant factors: Depth (Breslow), Mitotic index, Tumor-infiltrating lymphocytes, tumor growth pattern, Presence of second malignancy, CCI [REDACTED]

Baseline characteristics with respect to ECOG, vital signs, physical examinations, ECG and hematology/biochemistry will be part of Section 17 (Safety Evaluation).

